7.1.4 Data Handling Conventions and Transformations

7.1.4.1 Conversion of Categorical Values to Numerical Values

For non-PK data that are continuous in nature, certain categorical values will be converted to numerical values for calculating summary statistics. For non-PK data that are categorical in nature (i.e., all possible outcomes are categorical), no conversion from categorical values to numerical values will apply for calculating summary statistics, unless otherwise specified.

7.1.4.1.1 Handling of LLOQ and ULOQ

Non-PK data that are continuous in nature (e.g., safety lab tests) but are less than the LLOQ or above the ULOQ will be imputed as follows:

- A value that is 1 unit less than the LLOQ will be used to calculate descriptive statistics if the datum is reported in the form of “< x” (where x is considered the LLOQ). For example, if the values are reported as < 50 and < 5.0, values of 49 and 4.9, respectively, will be used to calculate summary statistics. An exception to this rule is any value reported as < 1 or < 0.1. For values reported as < 1 or < 0.1, a value of 0.9 or 0.09, respectively, will be used for calculating summary statistics.
- A value that is 1 unit above the ULOQ will be used to calculate descriptive statistics if the datum is reported in the form of “> x” (where x is considered the ULOQ). Values with decimal points will follow the same logic as above.
- The LLOQ or ULOQ will be used to calculate descriptive statistics if the data is reported in the form of “≤ x” or “≥ x” (where x is considered the LLOQ or ULOQ).
- “Occasional” will be assigned 1 unit less than the LLOQ. An exception to this rule is if LLOQ is 1 or 0.1, a value of 0.9 or 0.09, respectively, will be used for calculating summary statistics.

7.1.4.1.2 Handling of Other Special Characters

Non-PK data that are continuous in nature but have a “x – y” interval value will be imputed as best of “x – y” for baseline and worst of “x – y” for post-baseline as their continuous numeric value, if needed for calculating summary statistics.

Non-PK data that are continuous in nature but have “None” representing zero will be assigned 0, if needed for calculating summary statistics.

Non-PK data that are continuous in nature but have “ND (not done)”, “QNS (quantity not sufficient)”, “NR (no result(s))”, or “Non-evaluable” representing non-valuable or missing value will be assigned missing, if needed for calculating summary statistics.

7.1.4.1.3 Handling of Special Laboratory Categorical Data

For a laboratory test that is continuous in nature but only had numeric values present when the result was abnormal but absent when the result was normal (e.g., when urine protein was normal (i.e., negative or absent), no numeric value was present in data), the numeric value will be assigned 0 corresponding to a normal (negative or absent) test result, and it is not considered as missing or unknown.

7.1.4.2 Handling of Predose and Post-infusion

For vital signs and ECG data that collect measurements at multiple time points (predose, post-infusion, or “Not Applicable”) on a study drug administration day, the following rules apply for assigning the measurements to times, when applicable.

(1) For the assessments collected on Study Day 1:

- The entries on the corresponding electronic CRF (predose, post-infusion) will be used.
 - If the entry on the corresponding electronic CRF is “post-infusion”, the assessment will be assigned the analysis visit “Day 1 Postdose”. Measurement time points are not applicable for “Day 1 Postdose”.
 - If the entry on the corresponding electronic CRF is “predose”, it will be considered as a candidate for baseline, and the baseline selection rules apply. Measurement time points are not applicable for baseline.

(2) For assessments collected at a post-Study-Day-1 scheduled visit, in which study drug is administered per the Schedules of Assessments in the protocols, the entries on the corresponding electronic CRF (predose, post-infusion) will be used, if the date of assessment is prior to or on the last dose date.

(3) For post-Study-Day-1 visits at which study drug is not administered per the Schedules of Assessments in the protocols, including Week 3 (vital signs only), Unscheduled, EFU, SFU, and ET, “Not Applicable” will be assigned as the measurement time point.

(4) For assessments collected after the last dose date, “Not Applicable” will be assigned as the measurement time point. And this takes precedence over entries on the corresponding electronic CRF.

(5) For assessments collected prior to the first dose date, time points do not apply. And this takes precedence over entries on the corresponding electronic CRF.

7.1.4.3 Handling of Baseline Value being Zero

For an endpoint, the percent change from baseline (PCFB) at a post-baseline visit is calculated as follows:

$$((\text{post-baseline value} - \text{baseline value}) / \text{baseline value}) \times 100\%$$

If the baseline value is 0 and the post-baseline value is also 0, then the PCFB is set to 0. If the baseline is 0 and the post-baseline value is non-zero then the PCFB is set to missing.

7.2 Participant Disposition and Protocol Deviations

7.2.1 Participant Enrollment and Disposition

For LTE analysis using ATS-LTE, a summary of participant enrollment will be provided by individual AL002 15 mg/kg, 40 mg/kg, and 60 mg/kg, and the TC treatment groups, AL002 40 and 60 mg/kg combined group and AL002 total group for each country, as well as for each investigator within a country. The summary will present the number and percentage of participants dosed in the LTE Study. For each column, the denominator for the percentage calculation will be the total number of participants analyzed for that column.

For Integrated analysis using ATS, a summary of participant disposition will be provided by individual AL002 15 mg/kg, 40 mg/kg, and 60 mg/kg, and the placebo/TC treatment groups, AL002 40 and 60 mg/kg combined group, and AL002 total group. This summary will present the number of participants dosed in the LTE Study, and the number of dosed participants in each of the categories listed below:

- Ongoing study drug if applicable
- Completed study drug
- Discontinued study drug
- Reasons for premature discontinuation of study drug
- Ongoing study if applicable
- Completed study
- Discontinued study
- Reasons for premature discontinuation of study

For the status of study drug and study completion and reasons for premature discontinuation, the number and percentage of participants in each category will be provided. The denominator for the percentage calculation for the study drug completion/discontinuation and study completion/discontinuation will be the total number of participants in the corresponding analysis set.

By-participant data listings for participant disposition will be provided.

7.2.2 Protocol Deviations

Protocol deviations will be recorded separately from the clinical database. A blinded review of the deviation log, as well as a programmatic listing of protocol deviations to determine non-significant and significant protocol deviations, will be conducted prior to final database lock. All significant deviations in the LTE Study will be summarized by individual AL002 15 mg/kg, 40 mg/kg, and 60 mg/kg, and the TC treatment groups, AL002 40 and 60 mg/kg combined group, and AL002 total group. A by-participant data listing of all significant protocol deviations including categorization of deviations, as significant or non-significant, will be provided.

7.3 Demographics and Baseline Characteristics

Demographics and baseline characteristics specified in this section will be summarized by individual AL002 15 mg/kg, 40 mg/kg, and 60 mg/kg, and the TC treatment groups, AL002 40 and 60 mg/kg combined group, and AL002 total group.

7.3.1 Demographics, Social History, and Medical History

For LTE Analysis, demographics from the Core Study, unless updated in the LTE Study, will be summarized for the ATS-LTE. In other words, for demographics, if the value is missing from the LTE Study, the one from the Core Study will be used in its place, except for age at time of informed consent. The age at time of informed consent of the LTE Study will be summarized.

Weight, height and BMI refer to the Core baseline for Group T-T and LTE baseline for Group P-TC (refer to Section 7.1.2 for definition), and will be summarized by treatment group, AL002 40 and 60 mg/kg combined group, and overall for the ATS-LTE.

Social history, medical history, and medical and surgical treatment procedures will be listed for the LTE Analysis and the Integrated Analysis.

By-participant data listings will be presented for the ATS.

For the Integrated Analysis, demographics will be summarized as they are in the Core Study for the ATS. They will also be shown for the FAS.

7.3.2 Prior and Concomitant Medications

Concomitant medications will be summarized by ATC drug class Level 4 and preferred name using the number and percentage of participants for each treatment group, AL002 40 and 60 mg/kg combined group, and AL002 total group for the Non-e4/e4 Set.

A participant reporting the same medication more than once will be counted only once within each ATC drug class when calculating the number and percentage of participants who received that medication. Medications may appear under multiple ATC drug classes. The summary will be ordered alphabetically by ATC medical class and then by preferred name in descending overall frequency within each ATC medical class. For drugs with the same frequency, sorting will be done alphabetically.

All medications (other than per-protocol study drugs) will be provided in a by-participant data listing sorted by participant ID number and administration date in chronological order.

7.4 Safety Analyses

All safety endpoints will be summarized with the Integrated Analysis, unless otherwise specified. The selected safety endpoints that will be summarized with the LTE Analysis are specified in the respective sections.

All LTE Analysis for a safety endpoint will be based on the ATS-LTE, unless otherwise specified. All Integrated Analysis for a safety endpoint will be based on the Non-e4/e4 Set, unless otherwise specified. Analysis sets are defined in Section 5.

Analyses (including analysis sets that analyses will be conducted on) to be performed for each interim analysis (IA) are specified in Section 8.

Unless otherwise specified, CFB for Group T-T and placebo will be based on the Core baseline. CFB for Titration Cohort will be based on the LTE baseline. Baseline is defined in Section 6.1. Core baseline and LTE baseline are referred to as baseline for simplicity in this section.

Analysis visit window definitions are described in Section 7.1.1.2.1.

In the case of multiple values in an analysis visit window, data will be selected for analysis as described in Section 7.1.3.2, unless otherwise specified.

7.4.1 Descriptive Summaries of Safety Endpoints

7.4.1.1 LTE Descriptive Summaries of Safety Endpoints

The LTE descriptive summary of a safety endpoint will summarize the data collected in the LTE Study (plus Core baseline when applicable) with descriptive statistics, by individual AL002 15 mg/kg, 40 mg/kg, and 60 mg/kg, and the TC treatment groups, AL002 40 and 60 mg/kg combined group, and AL002 total group.

When applicable, for a continuous safety endpoint, the number of participants with safety outcomes, mean, SD, median, Q1, Q3, min, and max, at baseline (Core baseline for Group T-T and LTE baseline for the TC (refer to Section 7.1.2 for baseline definition)) and each analysis visit (based on Core Study Day for Group T-T and based on LTE Study Day for the TC), along with the CFB at each analysis visit, will be summarized.

The CFB for Group T-T will be based on the Core baseline, and the CFB for the TC will be based on the LTE baseline. And only analysis visits occurring in the LTE Study are included in the LTE Analyses.

By-participant data listings for safety data will be provided.

7.4.1.2 Integrated Descriptive Summaries of Safety Endpoints

The integrated descriptive summary of a safety endpoint including the Placebo Data will summarize all the data collected in the Core Study and in the LTE Study with descriptive statistics based on the Non-e4/e4 Set, by individual placebo, AL002 15 mg/kg, 40 mg/kg, and 60 mg/kg, and the TC treatment groups, AL002 40 and 60 mg/kg combined group, and AL002 total group.

The CFB will be based on the Core baseline for placebo, AL002 15 mg/kg, 40 mg/kg, and 60 mg/kg, and AL002 40 and 60 mg/kg combined treatment groups. The CFB for the TC will be based on the LTE baseline. And all analysis visits from the Core and LTE Studies will be included.

7.4.1.2.1 Integrated Descriptive Summaries of Safety Endpoints by Time Interval of Events Occurrence

Selected safety endpoints (as specified in Section 8) will be summarized by the categories of timing to occurrence of events since Core Study Day 1 (for Group T-T and placebo) or LTE Study Day 1 (for the Titration Cohort) in weeks: < 48 Weeks, $\geq 48 - < 96$ Weeks, $\geq 96 - < 144$ Weeks, and ≥ 144 Weeks. Timing to occurrence of events since Core Study Day 1 (for Group T-T and placebo) or LTE Study Day 1 (for the Titration Cohort) in weeks is calculated as the number of weeks between the Core/LTE Study Day 1 and event start date, i.e., timing to occurrence of events = (event start date - Core/LTE Study Day 1 + 1) / 7. In the event of missing or incomplete event start date, the same imputation rules as specified for the events apply.

7.4.2 Extent of Exposure to AL002

Duration of exposure to AL002, the total number of AL002 doses received, and treatment compliance as defined in Section 6.2.1 will be summarized by treatment group, AL002 40 and 60 mg/kg combined group, and overall.

Duration of exposure to AL002 will be summarized in days, weeks, months, and participant-years of exposure for both the LTE Analysis and the Integrated Analysis.

The total number of study drug doses received will be summarized as a continuous measure for both the LTE Analysis and the Integrated Analysis.

For the LTE Analysis, duration of LTE exposure to AL002 as specified in Section 6.2.1 and the total number of AL002 doses received will summarize the study drug administration of AL002 collected in the LTE Study. And duration of LTE exposure to AL002 in weeks will also be mapped to one of the following duration categories: < 16 weeks, 16 weeks - < 32 weeks, 32 weeks - < 48 weeks, 48 weeks - < 56 weeks, and ≥ 56 weeks, where 1 week = 7 days.

For the Integrated Analysis, duration of exposure to AL002 and the total number of AL002 doses received will summarize the study drug administration of AL002 collected across the Core Study and the LTE Study. And duration of exposure to AL002 in weeks will also be mapped to one of the following duration categories: < 16 weeks, 16 weeks - < 32 weeks, 32 weeks - < 48 weeks, 48 weeks - < 64 weeks, 64 weeks - < 80 weeks, 80 weeks - < 96 weeks, 96 weeks - < 112 weeks, 112 weeks - < 128 weeks, 128 weeks - < 144 weeks, 144 weeks - < 152 weeks, and ≥ 152 weeks.

Treatment compliance will be summarized as a continuous measure and will also be categorized as < 80%, 80% – 120%, > 120%.

Duration of exposure to AL002, the total number of AL002 doses received, and treatment compliance will be listed.

7.4.3 Adverse Events

AE related terms such as TEAE, SAE, and AESI are defined in Section 6.2.2.

An overall summary of AEs will present the number and percentage of participants who experienced at least 1 TEAE for the following events:

- TEAE (total and by maximum severity),
- Treatment-related TEAE (total and by maximum severity),
- TEAE leading to early study drug discontinuation,
- TEAE leading to study drug interruption,
- Treatment-emergent SAE,
- Treatment-related treatment-emergent SAE,
- Treatment-emergent AESI,
- Treatment-related treatment-emergent AESI,
- TEAE leading to death (i.e., outcome is fatal),

The number and percentage of participants who experienced at least 1 TEAE and the number and percentage of participants who experienced at least 1 treatment-related TEAE will be summarized by SOC, PT, and Severity. For other AEs described below, summaries will be provided by SOC and PT:

- TEAE (total and by severity),
- Treatment-related TEAE (total and by severity),
- TEAE leading to early study drug discontinuation,
- TEAE leading to study drug interruption,
- Treatment-emergent SAE,
- Treatment-related treatment-emergent SAE,

- Treatment-emergent AESI,
- Treatment-related treatment-emergent AESI,
- TEAE leading to death (i.e., outcome is fatal).

AEs will be summarized and listed first in alphabetic order of SOC and then by PT in descending order of total frequency within each SOC.

In addition to the above summary tables, TEAE, treatment-related TEAE, and treatment-emergent SAE will be summarized by PT only, in descending order of total frequency.

In addition to the by-participant data listing of all AEs, separate by-participant data listings will also be provided for the following:

- TEAE leading to early study drug discontinuation,
- Treatment-emergent SAE,
- Treatment-emergent AESI,
- TEAE leading to death.

For Integrated Analysis, all of the above summaries will be presented overall and also by the time intervals of event occurrence defined in Section 7.4.1.2.1. Denominators for percentages of events are determined by the numbers of participants at risk in each interval for each treatment group, which are those participants where $[\min(\text{last participation day, last dose date} + 90 \text{ days}) - \text{first dose date} + 1]/7$ is at least equal to the lower bound of the time interval.

For LTE Analysis, the following selected summaries will be provided for events during the LTE Study.

- Overall summary of AEs
- TEAEs by SOC and Preferred Term
- TEAE leading to study drug interruption,
- SAEs
- TEAE leading to death

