2. STUDY OBJECTIVES AND ENDPOINTS

The study objectives and endpoints are provided in [Table 2-1](#).

Table 2-1. Study Objectives, Endpoints and Estimands for LTE

| Primary Objectives | Primary Safety Endpoints and Primary Estimand |
|--|---|
| 
To evaluate the long-term safety and tolerability of AL002 in participants with AD.
 | 
Part 1: Primary Safety Endpoint and Estimand:
 
 • Treatment condition: Group T-T (AL002 15 mg/kg, 40 mg/kg or 60 mg/kg IV Q4W) continues their Core Study treatment in the LTE Study; Group P-TC treated with Placebo in the Core study will be titrated to 60 mg/kg of AL002 in the LTE study. • Target population: adult participants with AD excluding apolipoprotein E (APOE) epsilon 4 (e4)-homozygous (e4/e4) participants. • Primary endpoints: AESI incidence and SAE incidence over all weeks. • Accounting for intercurrent events: a composite strategy will be used to handle intercurrent events as below: 
 ○ Hypothetical strategy for handling premature study drug discontinuation for any reason (AEs with a start date more than 90 days after study drug discontinuation are not counted) ○ Treatment policy strategy for handling all other intercurrent events. • Population-level summaries: the descriptive statistical summaries for each treatment group of incidence rates for all AESIs and SAEs over similar periods of time. 
Part 2: Primary Safety Endpoints:
 
 • Changes from baseline (CFBs) in vital signs, physical findings, neurological findings, ophthalmological findings, ECG findings, and clinical laboratory results. • MRI abnormalities (ARIA events) • C-SSRS. 
Primary Estimand for Safety Endpoints Above:
 
The estimand for the Part 2 endpoints is defined with similar attributes as for the Part 1 estimand except applied to the different endpoints
 |

| Primary Objectives | Primary Safety Endpoints and Primary Estimand |
|--|---|

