3.2 Participant Grouping

There are two treatment classes for the LTE and Integrated Analyses:

- **Group T-T** includes participants who were exposed to AL002 during the Core Study. They will continue at their Core Study AL002 dosage during the LTE Study if enrolled in the LTE Study. Group T-T is further broken down as AL002 15 mg/kg, 40 mg/kg, and 60 mg/kg treatment groups.

- **Group P-TC** includes participants who were exposed only to placebo during the Core Study. They will be assigned to the TC during the LTE Study if enrolled in the LTE Study. Group P-TC might be separated into placebo and TC treatment groups depending on the summaries/analyses.

For Group P-TC, the data collected when the participants were receiving placebo in the Core Study might be summarized and/or analyzed separately from the data collected once the participants received the first study drug administration in the LTE Study. The data collected when the participants were receiving placebo in the Core Study up to the day before the participants received the first study drug administration in the LTE Study (separately from the data collected in the LTE Study) is referred to as **the Placebo Data** throughout the SAP. And it includes the data from the placebo participants who did not enroll in the LTE Study. The data collected on or after the day when the participants received the first study drug administration in the LTE Study is referred to as **the TC Data** throughout the SAP.

The first dose date of AL002 refers to the earliest date of any amount of AL002 administered across the Core Study and the LTE Study. **The last dose date of AL002** refers to the latest date of any amount of AL002 administered across the Core Study and the LTE Study. **The first dose date of any study drug** refers to the earliest date of any study drug administered, including placebo, across the Core Study and the LTE Study.

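### The by-interval adverse event percentages in SAP 7.4.3 ignore follow-up inside the interval, so two late cells (placebo at 96-144 weeks, Titration Cohort at 48-96 weeks) are not comparable with Group T-T

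*SAP*

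**What the plan says.** On the scope of the tables, SAP 7.4.3 states: "For Integrated Analysis, all of the above summaries will be presented overall and also by the time intervals of event occurrence". The intervals come from SAP 7.4.1.2.1: below 48, 48 to below 96, 96 to below 144, and 144 weeks or more. There, selected endpoints "will be summarized by the categories of timing to occurrence of events since Core Study Day 1" for Group T-T and placebo, and since LTE Day 1 for the Titration Cohort.

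On the denominator, 7.4.3 states: "Denominators for percentages of events are determined by the numbers of participants at risk in each interval". It computes each participant's follow-up as the earlier of last participation and last dose plus 90 days, counted from first dose. It includes the participant if this "is at least equal to the lower bound of the time interval". Time spent inside the interval does not enter.

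SAP 7.4.1.2 sets the columns next to each other: "by individual placebo, AL002 15 mg/kg, 40 mg/kg, and 60 mg/kg, and the TC treatment groups", plus pooled groups. SAP 3.2 ends the Placebo Data early, since they run only "up to the day before the participants received the first study drug administration in the LTE Study".

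The primary safety estimand in SAP Table 2-1 (Part 1) asks for "incidence rates for all AESIs and SAEs over similar periods of time". Participant-years appear in SAP 7.4.2 as an exposure summary. No adverse event rate uses them.

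**The concern.** A percentage with at least one event depends on how long people are watched. If one column is watched for 4 weeks of a 48-week interval and its neighbour for all 48, the percentages differ several-fold even when the risk is the same.

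Long-term safety is a primary objective, and AESI and SAE incidence are the Part 1 primary endpoints. Read across, the late cells would suggest an excess on continued AL002 over placebo, and fewer events in the Titration Cohort than in Group T-T, from unequal time at risk alone. The same interval tables are already planned for the first interim analysis (SAP 8.1.3).

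**Working it through.** **Calendar inputs, and a check against the SAP's own days**
- LTE: 13 doses every 4 weeks, then the final visit 8 weeks later (SAP 6.2.1; protocol 3.2.4). (13 − 1) × 4 + 8 = 56 weeks, as in SAP 3.1.
- LTE Week 48 is day 12 × 28 + 1 = 337, and the final visit is day 337 + 56 = 393. Both match the LTE visit windows.
- Core dosing lasts up to 96 weeks (protocol 1.2.2), and the first LTE dose follows 4 weeks ± 5 days after the last Core dose (SAP 3.1). LTE Day 1 is therefore about Core Week 100, day 701, and the LTE final visit is Core day 701 + 392 = 1093. Both match the Core-day windows.

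**Completers' follow-up in each interval** (SAP timing is study day ÷ 7, so the lower bounds fall on days 336, 672 and 1008)
- Placebo, 96-144 weeks: days 672 to 700 = 29 days = 4.1 weeks (3.4 to 4.9 with ± 5 days).
- Titration Cohort, 48-96 weeks: LTE days 336 to 393 = 58 days = 8.3 weeks.
- Group T-T: 336 days = 48 weeks in each interval.

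**Expected percentages at equal risk.** Event rates are not in the documents. Assume one constant hazard in all groups, with a proportion p having an event per 48 weeks. The expected proportion over t weeks is f(t) = 1 − (1 − p)^(t/48). The table uses t = 4 and t = 8.

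| p (Group T-T, 48 weeks) | Placebo, 4 weeks | Ratio T-T/placebo | Titration Cohort, 8 weeks | Ratio T-T/Titration Cohort |
|---|---|---|---|---|
| 5% | 0.43% | 11.7 | 0.85% | 5.9 |
| 10% | 0.87% | 11.4 | 1.74% | 5.7 |
| 20% | 1.84% | 10.9 | 3.65% | 5.5 |
| 50% | 5.61% | 8.9 | 10.91% | 4.6 |
| 80% | 12.55% | 6.4 | 23.53% | 3.4 |

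**Relaxing the completer assumption** (p from 5% to 80%; the scenarios are assumptions)
- Roll-over proportion r of 80% to 90% (the range in SAP 3.5), with the rest followed 8 or 13 weeks in the interval in both arms. A last dose at Week 96 plus 90 days gives 13.1 weeks. The ratio is [r·f(48) + (1 − r)·f(n)] ÷ [r·f(4) + (1 − r)·f(n)], where n is 8 or 13. It runs from 71.07% ÷ 17.11% = 4.15 (r = 0.8, n = 13, p = 80%) to 9.78 (r = 0.9, n = 8, p = 5%).
- Roll-over spread evenly over Core Weeks 48 to 100, which shortens Group T-T time in 96-144 weeks: T-T/placebo 4.95 to 7.93.
- 30% of Group T-T leaving evenly across the interval: T-T/placebo 5.66 to 9.98, T-T/Titration Cohort 3.02 to 5.00.

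**Overall column.** At p = 10%, completers followed 156, 100 and 56 weeks give 1 − 0.9^(156/48) = 29.0%, 1 − 0.9^(100/48) = 19.7% and 1 − 0.9^(56/48) = 11.6%. The ratios are 29.0 ÷ 19.7 = 1.5 and 29.0 ÷ 11.6 = 2.5. The AL002 total group pools the Titration Cohort with Group T-T (SAP 7.1), so it mixes the 56- and 156-week follow-ups.

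**Placebo bound.** The denominator formula has no stop at LTE Day 1. Take a last Core dose at Week 86 (day 603) and LTE start at Week 90. Last dose plus 90 days is day 693, and 693 ÷ 7 = 99 weeks. If last participation is read across both studies, this person enters the 96-144 placebo denominator with no placebo time there.

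**With person-time as denominator.** At p = 20%, the rate is −ln(0.8) ÷ 48 × 52.18 = 0.243 per participant-year in every group, a ratio of 1.0.

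**The case against.** Much can be said for the plan, and several points stand.
- The tables are descriptive. SAP 3.4 names two hypotheses, on CDR-SB and on first ARIA events, and neither uses these percentages. This stands.
- Splitting by interval is itself a way to compare similar periods. It works below 48 weeks for all groups, and at 48-96 weeks for Group T-T versus placebo. This stands, and it confines the problem to two cells plus the overall column.
- Ratios of 11.4 and 5.7 (p = 10%) describe full completers. The Non-e4/e4 Set includes dropouts and people who never enter the LTE, and at an early interim cut-off Group T-T follow-up is short too. This stands as to size. In the scenarios above, the gap still does not fall below about 4-fold for placebo or 3-fold for the Titration Cohort.
- A constant hazard is doubtful for ARIA. Protocol 1.4 describes, from anti-amyloid trials, more ARIA early in treatment and less later. Where the hazard falls within an interval, the weeks actually observed carry more than their share of events and the ratio shrinks. The figures illustrate the effect and do not forecast it.
- Against placebo, the distortion makes AL002 look worse, so it does not hide harm there. This is true, but a spurious excess is still a wrong safety message.
- Rates from about 4 weeks of placebo time will rest on few events. This is true, and is a reason to show the person-time as well.

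A reader might also infer that placebo columns contain events that occurred on AL002. The documents do not support this: SAP 3.2 ends Placebo Data before the first LTE dose, and SAP 7.4.3.1 counts the two periods separately. The missing cap affects the denominator only.

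**Conclusion.** The point holds for two cells of the descriptive integrated tables, and in milder form for the overall column. At an equal constant hazard of 5% to 80% per 48 weeks, Group T-T would appear roughly 4 to 12 times worse than placebo at 96-144 weeks and 3 to 6 times worse than the Titration Cohort at 48-96 weeks. The low ends come from the roll-over and dropout scenarios, and the high ends from completers with rare events. In those cells the SAP does not meet its own standard of similar periods.

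A reader might infer that the plan builds in a false advantage for slow titration. The documents do not support that for the titration objective. SAP 7.4.8 compares the first 48 weeks in both groups by the CMH method and adds Kaplan-Meier curves with censoring. Titration takes 24 or 32 weeks (SAP 3.1), so the 48-96 week cell lies after it. Nor do the documents support the claim that every by-interval percentage is unbalanced.

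**What to change.** In SAP 7.4.3 and 7.4.1.2.1:
- Beside the percentages for TEAEs, SAEs and AESIs, overall and by interval, add the person-time per cell and the exposure-adjusted incidence (participants with a first event per 100 participant-years at risk within the interval).
- End person-time at the earliest of first event, interval end, last participation, last dose plus 90 days and, for placebo, LTE Day 1 minus 1. Apply the same placebo cap in the denominator rule.
- Keep the percentages, with a footnote that placebo at 96-144 weeks and the Titration Cohort at 48-96 weeks are not comparable across groups.

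The cost is SAP wording and extra columns, since 7.4.3 already derives each participant's follow-up. The rates assume a roughly constant hazard within an interval and will be imprecise where person-time is short. Suppressing the late percentages is not needed.
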